4.9.4 Safety Analysis

Information on the timing, severity, relationship to drug, relationship to therapy, effect on therapy, and degree of seriousness of adverse events will be collected from and summarized for all patients.

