3.4 SAFETY PLAN

Patients will be evaluated at each study visit for the duration of their participation in the study (see Section 4.5 and Appendix A, Study Flowchart).

Protocol: Ocrelizumab Providence Health & Services

Page 6 of 34 ML39655

A full neurologic examination will be conducted at every visit (may be historical at screening if an exam was completed within 28 days prior to consent, and may be waived at baseline if screening and baseline are 7 or less days apart). Any worsening or new abnormality (including laboratory results) that is determined by the investigator as clinically significant will be recorded as an AE and will be monitored until resolution or stabilization. MS related symptoms are not to be reported as AEs unless, in the opinion of the investigator, the symptoms are unusually serious and relevant.

The recommendation from the OCR prescribing information dated 11/2018 is to pre-medicate with 100mg of methylprednisolone (or an equivalent corticosteroid) administered intravenously approximately 30 minutes prior to each OCR infusion to reduce the frequency and severity of infusion related reactions (IRRs) [see Warnings and Precautions (5.1) in prescribing information]. Also, it is recommended to pre-medicate with an antihistamine (e.g., diphenhydramine) approximately 30-60 minutes prior to each OCR infusion to further reduce the frequency and severity of infusion reactions.

Recommended medications to be available if there is an infusion reaction (per treating investigator discretion):

- A. Epinephrine – anaphylaxis
- B. Albuterol – bronchospasm or hypoxia
- C. Famotidine 20mg IV – hives, itching, or anaphylaxis
- D. Oxygen therapy – shortness of breath, chest pain, or hypoxia
- E. Acetaminophen – pain, fever, and headaches
- F. Methylprednisolone – hives, itching, shortness of breath, or anaphylaxis

Patients administered a sedating antihistamine for the treatment or prevention of IRRs should be given appropriate warnings concerning drowsiness and potential impairment of ability to drive or operate machinery.

Pre-medications, infusion reaction management, and infusion reaction medications are to be left to treating investigator discretion.

Suggested Management of IRRs

Severe IRRs

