- Concomitant medications and adverse events (not required to be reviewed with the patient in person if Baseline is within 7 days of Screening visit, collect via chart review)
- OCR administration (300mg, 2 administrations: Day 0 and Day 14 ± 2 days)

Visit 3/3 Month Visit (Day 84 +/- 14 days from Baseline Day 0)

The following clinical and laboratory evaluations will occur 84 days from Baseline with a +/- 14 day window.

- Vital signs
- Neurological exam
- Relapse assessment
- EDSS
- Laboratory assessments: CBC, CMP, Pregnancy test (female only)
- MRI
- Concomitant medications and adverse events

Visit 4/6 Month Visit (Day 168 +/- 14 days from Baseline Day 0)

The following clinical and laboratory evaluations will occur 168 days from Baseline with a +/- 14 day window.

- Vital signs
- Neurological exam
- Relapse assessment
- EDSS
- MSIS-29
- Laboratory assessments: CBC, CMP, Pregnancy test (female only)
- MRI
- Concomitant medications and adverse events
- OCR administration (600mg)

Visit 5/9 Month Visit (Day 252 +/- 14 days from Baseline Day 0)

The following clinical and laboratory evaluations will occur 252 days from Baseline with a +/- 14 day window.

- Vital signs
- Neurological exam
- Relapse assessment
- EDSS
- Laboratory assessments: CBC, CMP, Pregnancy test (female only)
- Concomitant medications and adverse events

Visit 6/12 Month Visit (Day 336 +/- 14 days from Baseline Day 0)

The following clinical and laboratory evaluations will occur 336 days from Baseline with a +/- 14 day window.

- Vital signs
- Neurological exam
- Relapse assessment
- EDSS
- MSIS-29
- Laboratory assessments: CBC, CMP, Pregnancy test (female only)
- MRI
- Concomitant medications and adverse events
- OCR administration (600mg)

End of Study (EOS) Phone Contact (30 days +/- 14 days from study discontinuation)

The following clinical evaluation will occur 30 days +/- 14 days from study completion (12 Month OCR administration) or premature termination visit:

- Adverse events

Premature Termination Visit

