5. REPORTING OF ADVERSE EVENTS

An AE is an unfavorable unintended sign, symptom, or disease that is experienced by the patient, whether or not there is a causal relationship with OCR. At the time of consenting, each patient will be given the names and telephone numbers of the study personnel for reporting AE's. The investigator must conduct thorough assessment to determine the severity of the AE and the relationship to the study drug. Any clinically significant AE of severity moderate or higher, requires follow up until resolution or stabilization by the treating investigator beyond the end of study contact.

All AEs should be recorded in the patient's AE case report form regardless of severity or relationship to the study drug. The investigator must review the laboratory findings for significance (all out of range values must be assessed as clinically significant or not clinically significant) and sign and date the laboratory report. All clinically significant laboratory findings must be reported as adverse events.

Any severe laboratory abnormalities that are considered serious should be reported to the coordinating center as outlined below.

All SAEs must be reported by the investigator to Genentech by email [contact] or [contact] and Providence Regional Research Regulatory Office by email [contact] (Regulatory) and CC [contact] (Study Manager) or fax to [contact] (Regulatory) and [contact] (Study Manager) within 24 hours of the investigator's knowledge of the event.

Severity

The intensity of severity of an AE will be graded as follows:

Mild	Symptoms(s) barely noticeable to subject or does not make subject uncomfortable; does not influence performance or functioning; prescription drug not ordinarily needed for relief of symptoms(s) but may be given because of personality of subject
Moderate	Symptom(s) of a sufficient severity to make subject uncomfortable; performance of daily activity is influenced; subject is able to continue in study; treatment for symptom(s) may be needed.
Severe	Symptom(s) cause severe discomfort; symptoms cause incapacitation or significant impact on subject's daily life; severity may cause cessation of treatment with investigational drug; treatment for symptom(s) may be given and/or subject hospitalized.

Relationship to Study Drug

The relationship or association of the AE to a study drug will be characterized as follows:

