Any AE that results in hospitalization or prolonged hospitalization should be documented and reported as an SAE. If a subject is hospitalized to undergo a medical or surgical procedure as a result of an AE, the event responsible for the procedure, not the procedure itself, should be reported as the SAE. For example, if a subject is hospitalized to undergo coronary bypass surgery, record the heart condition that necessitated the bypass as the SAE.

Hospitalizations for the following reasons do not require reporting:

- Hospitalization or prolonged hospitalization for diagnostic or elective surgical procedures for preexisting conditions
- Hospitalization or prolonged hospitalization required to allow efficacy measurement for the study or
- Hospitalization or prolonged hospitalization for scheduled therapy of the target disease of the study.

e. Assessment of Severity of Adverse Events

The adverse event severity grading scale for the NCI CTCAE (v5.0) will be used for assessing adverse event severity. The below table should be used for assessing severity for adverse events that are not specifically listed in the NCI CTCAE.

Adverse Event Severity Grading Scale for Events Not Specifically Listed in NCI CTCAE

Grade	Severity
1	Mild; asymptomatic or mild symptoms; clinical or diagnostic observations only; or intervention not indicated
2	Moderate; minimal, local, or non-invasive intervention indicated; or limiting age-appropriate instrumental activities of daily living ^a
3	Severe or medically significant, but not immediately life-threatening; hospitalization or prolongation of hospitalization indicated; disabling; or limiting self-care activities of daily living ^{b,c}
4	Life-threatening consequences or urgent intervention indicated ^d
5	Death related to adverse event ^d

NCI CTCAE = National Cancer Institute Common Terminology Criteria for Adverse Events.

Note: Based on the most recent version of NCI CTCAE (v5.0), which can be found at: http://ctep.cancer.gov/protocolDevelopment/electronic_applications/ctc.htm

- a. Instrumental activities of daily living refer to preparing meals, shopping for groceries or clothes, using the telephone, managing money, etc.
- b. Examples of self-care activities of daily living include bathing, dressing and undressing, feeding oneself, using the toilet, and taking medications, as performed by patients who are not bedridden.

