Following Case Transmission Verification, single case reports which have not been received by Genentech shall be forwarded by Providence Brain and Spine Institute to Genentech within five (5) calendar days from request by Genentech.

At the end of the study, a final cumulative Case Transmission Verification report will be sent to Genentech.

i. AEs of Special Interest (AESIs)

AESIs are a subset of Events to Monitor (EtMs) of scientific and medical concern specific to OCR, for which ongoing monitoring and rapid communication by the Investigator to the Sponsor is required. Such an event might require further investigation in order to characterize and understand it. Depending on the nature of the event, rapid communication by the trial Sponsor to other parties (e.g., Regulatory Authorities) may also be warranted.

There are no ocrelizumab Events of Special Interest.

Adverse events of special interest for this study include the following:

- Cases of potential drug-induced liver injury that include an elevated ALT or AST in combination with either an elevated bilirubin or clinical jaundice, as defined by Hy's law:
 - Treatment-emergent ALT or AST $> 3 \times$ ULN in combination with total bilirubin $> 2 \times$ ULN
 - Treatment-emergent ALT or AST $> 3 \times$ ULN in combination with clinical jaundice
- Data related to a suspected transmission of an infectious agent by the study drug (STIAMP), as defined below:

Any organism, virus, or infectious particle (e.g., prion protein transmitting transmissible spongiform encephalopathy), pathogenic or non-pathogenic, is considered an infectious agent. A transmission of an infectious agent may be suspected from clinical symptoms or laboratory findings that indicate an infection in a patient exposed to a medicinal product. This term applies only when a contamination of the study drug is suspected

j. Exchange OF Single Case Reports

Providence Brain and Spine Institute will be responsible for collecting all protocol-defined Adverse Events (AEs)/Serious Adverse Events (SAEs), AEs of Special Interest (AESIs), Special Situation Reports (including pregnancy reports) and Product Complaints (with or without an AE) originating from the Study for the Product.

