J: Review results for potential AEs.

K: At Visit #1, report any clinically significant findings as medical history. At all other applicable visits, report clinically significant findings as AEs.

L: May be historical MRI, if completed within 6 weeks prior to Baseline (Day 0). Recommended to be completed after last dose of NTZ. Must be prior to first dose of OCR at Day 0.

M: MRI to be completed and reviewed by investigator prior to OCR administration.

N: Subjects should be informed that they should expect to be at infusion up to one full day for each dose. See section 4.3.1 for pre-medication instructions.

O: At Visit #1, also review all prior medications taken within last 4 weeks and all prior lifetime MS disease modifying therapies.

P: Metabolic Panel to include: Total Bilirubin, ALT, AST, Urea, Creatinine, Calcium, Sodium, and Potassium.

Q: CBC to include: Hemoglobin, Hematocrit, RBCs, WBC Absolute and Differential, Absolute Neutrophil Count (ANC), Absolute Lymphocytes, and Quantitative Platelet Count.

R: To include JCV index, status, and date of most recent result. JCV laboratory is not being collected at screening visit.

S: Vitals assessment to include: weight, BP, HR, oral temperature, RR. Height also to be recorded at screening.

T: Full EDSS not required at screening, but investigator must confirm subject's estimated EDSS is not greater than 6 based on the most recent neurologic exam. If screening is within 7 days prior to 1st dose of OCR, a full EDSS must be completed at Screening. Full EDSS will be required at all subsequent visits.

U: Data for this assessment may be collected from historical clinical record if completed within prior 28 days (inclusive) of subject informed consent form signature date. If not available, completed at screening visit.

V: Data for this assessment may be collected from historical clinical record if completed within prior 6 months (inclusive) of subject informed consent form signature date. If not available, completed at screening visit.

W: Day 0 is defined as the day of administration of the 1st dose of OCR. Other Baseline procedures may be completed up to 7 days prior to 1st dose (Day -7 to Day 0).

Y: If Screening visit falls within 7 days prior to 1st dose OCR (Day -7 to Day 0), these procedures do not need to be repeated. Pregnancy test should be done at baseline if historical test used for screening visit.

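### Blood counts and liver tests are taken at the scheduled clinic visits, but section 4.9.4 summarises adverse events only; a numeric laboratory summary would be a cheap improvement.

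*Combined protocol and SAP*

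**What the plan says.** **Collection.** Section 4.5.1 and Appendix A schedule a CBC and a metabolic panel at screening, baseline, months 3, 6, 9 and 12, and premature termination. The baseline panel may be skipped when screening was within 7 days. At unscheduled visits panels are drawn only if indicated, and the end-of-study phone contact has none. Appendix A footnote Q lists among the CBC contents "WBC Absolute and Differential, Absolute Neutrophil Count (ANC), Absolute Lymphocytes, and Quantitative Platelet Count". Footnote P reads "Metabolic Panel to include: Total Bilirubin, ALT, AST, Urea, Creatinine, Calcium, Sodium, and Potassium".

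**Analysis.** Section 4.9.4 is a single sentence covering several attributes of adverse events, ending with the "degree of seriousness of adverse events will be collected from and summarized for all patients".

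**Route from laboratory value to adverse event.** Section 3.4 says that a worsening or new abnormality, laboratory results included, "that is determined by the investigator as clinically significant will be recorded as an AE". Section 5 has the investigator classify every out-of-range value as clinically significant or not and sign the report; then "All clinically significant laboratory findings must be reported as adverse events".

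**Numeric exception.** Section 5.3 i lists as events of special interest "Cases of potential drug-induced liver injury that include an elevated ALT or AST", defined as ALT or AST above 3 x ULN with total bilirubin above 2 x ULN or with clinical jaundice.

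**Grading.** Section 5.3 e states "The adverse event severity grading scale for the NCI CTCAE (v5.0) will be used for assessing adverse event severity".

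**The concern.** The panels measure things that the protocol itself treats as relevant to safety. OCR acts by destroying B lymphocytes (section 1), infections are an ancillary safety outcome (section 3.3.3), and drug-induced liver injury is of special interest (section 5.3 i). Yet the plan never looks at the measured values as data. What gets reported is the subset of abnormalities that an unblinded investigator judged to matter, in a single-group study at 5 centers.

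At stake is what the trial can say about blood counts and liver enzymes after the switch. As written, it could report how many laboratory findings were called adverse events. It has no planned statement of how far lymphocytes or neutrophils fell, or how many patients reached a given CTCAE grade. The primary endpoint is not touched.

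**Working it through.** **1. Does any part of the plan analyse laboratory values?**
- Section 3.3.2 (secondary outcomes): the safety items are AE and SAE counts and OCR discontinuation.
- Section 3.3.3 (ancillary safety outcomes): infusion reactions and infections.
- Section 4.9.3: relapse, MRI, EDSS and MSIS-29. The sentence promising summary statistics for continuous and categorical variables stands under Efficacy Analysis and names no laboratory variable.
- Section 4.9.4: adverse events only.
- Section 4.9.5: relapse, ARR, EDSS, MSIS-29 and patient characteristics.

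None of these contains a laboratory summary, change from baseline, shift table or grade count.

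**2. What must happen for a value to reach the results?**

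| Laboratory change | Route into the 4.9.4 summary |
|---|---|
| Neutrophils, lymphocytes, platelets, any size | Investigator's call of clinical significance (3.4, 5) |
| ALT, AST or bilirubin below the Hy's-law combination | Same call |
| ALT or AST > 3 x ULN with bilirubin > 2 x ULN, or with jaundice | Special-interest event by definition (5.3 i) |

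CTCAE grading under 5.3 e applies to adverse events, so in the first two rows it comes after the call. Section 5.1 speaks of events considered related to OCR, but section 5 requires recording whatever the relationship, so I do not count relatedness as a second filter.

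**3. How much data has no planned analysis?** Inputs: 50 patients and 10% attrition (section 4.9.6); four post-baseline visits with panels (section 4.5.1).
- The plan's 50 reproduces: 45 / (1 - 0.10) = 50.
- Upper limit: 50 x 4 = 200 panels of each type.
- With 5 dropouts who all leave before month 3: 45 x 4 = 180. If all 5 leave after month 9: 180 + 5 x 3 = 195.

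These counts leave out premature-termination and unscheduled panels and assume no missed visits.

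**4. Can under-reporting be sized?** That needs the true frequency of graded laboratory changes and the share that investigators would flag. The documents give neither, so any figure would only restate what was assumed. I give none.

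**5. What would change from baseline mean?** Section 3.2 cites NTZ as undetectable 8 weeks after the last infusion, while OCR starts at 4 to 6 weeks. A panel drawn on Day 0 is thus 2 to 4 weeks short of that point. The month 3 visit (Day 84 ± 14) falls at the earliest 28 + 70 = 98 days, or 14 weeks, after the last NTZ dose. The baseline value may therefore be taken with NTZ still present, and every scheduled later value comes after the 8-week point. With no control group, washout and OCR effect cannot be separated.

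**The case against.** The strongest reply is that the analysis matches the objective. Section 2.2 defines safety through adverse events and discontinuation, and no listed safety outcome is a laboratory measure. That stands: a reader might infer that the secondary safety objective goes unanswered, and the documents do not support this. The tables would add to the answer.

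Second, section 5 requires a documented call on every out-of-range value, so abnormalities are reviewed. This is a real control, but the call remains a judgement, and only the positive calls enter the summary.

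Third, a reader might infer that all liver signals depend on that judgement. Section 5.3 i rules this out for Hy's-law cases.

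Fourth, one might infer that reported rates will be too low by some amount, or will differ between centers. The documents hold no data on either.

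Fifth, hepatitis B testing is scheduled only at screening, and one might want to tie that to this point. It concerns clinical monitoring, which end-of-study tables would not alter.

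Last, it is not certain that numeric values are in the database. Section 6.5 describes data entry in general terms, and Appendix A marks the CBC and metabolic panel as study-paid at baseline but not at months 3 to 12. Footnote U does treat these panels as a source of study data. The objection stands as a cost to be confirmed. If the values are held, a later listing remains possible, so what is lost is prespecification.

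**Conclusion.** The point holds as a cheap improvement to the safety analysis. The plan schedules CBC and liver tests but prespecifies no summary of them. Blood-count changes, and liver changes below the Hy's-law thresholds, enter the results only through an open-label investigator's call. Up to 200 scheduled post-baseline panels of each type are affected; at the planned attrition the count is 180 to 195, depending on when patients leave. The size and direction of any distortion in reported rates cannot be derived from the documents.

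The conclusion rests on reading 4.9.4 as the complete safety analysis. Its benefit rests on numeric results being recorded or recordable.

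**What to change.** Add to section 4.9.4, for all patients who received at least one OCR infusion:

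- (a) Values by visit, and change from the last pre-OCR value, for ANC, absolute lymphocytes, platelets, ALT, AST and total bilirubin. Using the last pre-OCR value also covers the baseline waiver.
- (b) Baseline-to-worst shift tables for the same tests, with CTCAE v5.0 grades computed from the numbers whatever the investigator's significance call.
- (c) Optionally, a programmed check of all visits against the thresholds already in section 5.3 i.
- (d) Optionally, a listing of infections beside the nearest ANC and lymphocyte values.

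Keep the adverse-event summary. Say that CTCAE v5.0 is used for the laboratory grades, because section 5 also carries a mild/moderate/severe scale. Naming the population also helps: section 4.9.1 evaluates safety in patients who followed protocol, while 4.9.4 refers to all patients. State beside (a) and (b) that the pre-OCR value may be taken while NTZ is still present, so change from baseline mixes NTZ washout with OCR effect.

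Cost: analysis-plan wording and a few tables, with no new visits or blood draws and no change to the sample size. Numeric values and local reference ranges must be entered if they are not already. Reported laboratory abnormality rates may look higher than under the adverse-event summary alone.

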4.9.5 Missing Data

Demographic information and baseline disease for patients who followed protocol and completed the study, violated protocol, and discontinued the study will be reported separately and compared. The reasons for discontinuing or violating protocol and the patient's time on drug at occurrence will be reported and any influence on the trial results will be discussed. To assess the comparability between centers, summaries will be reported for all patients overall and by study center. Any other irregularities that result in missing data will be fully identified and discussed.

For the per protocol and full analysis sets, missing data due to discontinuation will be incorporated as censored time points in the survival analysis of relapse-free patients and ARR will be calculated using the range of time that the individual was in the study. If interim time points at 3, 6, or 9 months are missing, only the time points available will be used in the survival analysis. No relapse data will be missing at baseline, since only patients relapse free for six months are included. For the Kaplan Meier analyses and

log rank tests stratified by age, gender, EDSS, and center, we expect these patient characteristics to be non-missing. However, if they are missing, a complete case analysis per variable will be used and the number of missing will be reported.

For the analysis of the change in EDSS and MSIS-29, a complete case analysis with per protocol patients will be used.

